6.2.2 Descriptive analyses

Rates of graft loss and death will also be summarized.

6.2.3 Statistical model, assumptions and hypotheses

Graft loss, death, graft loss or death and antibody-treated biopsy proven acute rejections will be analyzed in a similar way to the tBPAR and time to tBPAR, although without the non-inferiority test. Other efficacy variables displayed in Table 6-1 will be presented within frequency tables to show the proportion of events and the CFZ533 treatment arm event rate will be compared with the control arm event rate using Z-statistics based on two-sided confidence intervals for differences in event rates.

6.2.3.1 Graphical presentation of results

The free CD40 and total CD40 on whole blood B cells data will be presented graphically to show the arithmetic mean (SD) of free and total CD40 on whole blood B cells compared to mean pre-dose over time (%), overlaid patient profiles of free CD40 and total CD40 on whole blood B cells compared to mean pre-dose over time and overlaid profiles of free CD40 on whole blood B cells based on total CD40 (%). Arithmetic mean (SD) of free CD40 on whole blood B cells based on total CD40 (%), arithmetic mean (SD) free CD40 decrease on B cells compared to mean pre-dose (%) and arithmetic mean (SD) free CD40 decrease on B cells compared to mean pre-dose (based on total CD40 available on B cells) (%) will also be presented. Additional overlaying individual profile plots of free CD40 decrease on B cells compared to mean pre-dose (%) and free CD40 decrease on B cells compared to mean pre-dose (based on total CD40 available on B cells) (%) will also be presented.

Corporate Confidential Information

Total soluble CD40 and total soluble CD154 data will be presented graphically in the form of individual patient panel plots by parameter, arithmetic mean (SD) over time plots and a panel plot presenting the soluble CD40, soluble CD154 for each patient separately.

Corporate Confidential Information

7 Statistical methods for safety and tolerability data

7.1.1 Variables

Adverse events, vital signs (blood pressure, pulse rate, body temperature), ECG intervals, laboratory measurements, as well as patient demographics, baseline characteristics, and treatment information.

The following B-cell subsets are also used as safety markers: mature B cells, naive B cell, transitional B cells, memory B cells, plasma cells, plasma blasts. Overlaid patient profiles for each of these markers over time shall be presented graphically.

7.1.2 Descriptive analyses

Patient demographics and other baseline characteristics

All data for background and demographic variables will be listed by treatment group and patient. Patient demographics will include age, sex, race, ethnicity, height, weight and BMI. Other baseline characteristics that shall be listed include relevant medical history, current medical conditions, results of laboratory screens, transplant history, donor characteristics (e.g., age, sex, race, type, CIT) and any other relevant information.

Summary statistics will be presented for the patients in the Full analysis set. Continuous variables will be presented with mean, median, standard deviation, minimum and maximum, and the number of non-missing observations.

Categorical data will be displayed via absolute and relative frequencies for each category (including a category labeled as “missing” when appropriate).

Table 7-1 Demographic variables and disease characteristics

Variable
Recipient demographics:
Age (continuous and categorized (< 50, \geq 50) and (< 65, \geq 65))
Gender
Race
Ethnicity
Vital signs at baseline:
Height
Body weight
BMI
Pulse (bpm)
Systolic blood pressure, Diastolic blood pressure (mmHg)
Donor demographics:
Age (continuous and categorized (< 50, \geq 50) and (< 65, \geq 65))

Variable

Gender

Race

Ethnicity

Donor characteristics:

Donor category (living related, living unrelated, deceased heart beating)

Hypotension prior to procurement (no, yes, unknown)

Donor and recipient serology:

EBV, CMV (negative, positive, not done)

HCV Ab, HBsAG, HBsAb, HCV RNA (negative, positive, not done)

Recipient background information:

End stage disease leading to transplantation

Current dialysis (yes/no)

Time since continuous dialysis first started

Number of previous kidney transplantations

Number of previous blood transfusions

Total number of HLA mismatches across Loci A, B, and DR
(categorical: 0, 1, 2)

Recipient/donor gender combination

Recipient/donor race combination

Transplantation procedure:

Cold ischemia time (deceased donors only: continuous and
categorized: < 12 hours, ≥ 12 to 24 hours, ≥ 24 to 30 hours, > 30
hours)

Study medication

Data for CFZ533 administration and concomitant therapies will be listed by treatment group and patient. The duration (days) of CFZ533 study medication administration will be summarized and listed. The duration will be calculated by subtracting the date of the last administration of study medication from the date of first administration and then adding the dosing interval for CFZ533. In calculating the duration of treatment, days of temporary interruption of study medication for any reason will be included, i.e, any days of interruptions will not be excluded from the duration of treatment. Further, the frequency of dose changes (including temporary dose interruption) will be presented by reason for the change.

Average daily doses of each treatment will be presented in a summary table and will be listed by treatment and patient. “Zero” will be used for periods of temporary interruption of study medication for any reason.

The number and percentage of patients who prematurely discontinued study medication will be summarized by reason for discontinuation.

If the number of events allow, Kaplan-Meier (KM) estimates of time to discontinuation of study medication curve will be constructed and presented graphically. In this analysis, patients

who have not discontinued study medication will be censored with the censoring time as defined by the last contact day.

Concomitant immunosuppressants

The dose of administered Basiliximab, MMF, Tac and CS will be listed by treatment and patient.

The dose of antibodies used for the treatment of acute rejection episodes will be summarized by treatment and listed by treatment and patient.

Other co-medications

Concomitant medications, other than immunosuppressants and CS mentioned above, will be listed by patient and summarized by therapeutic class and preferred term by presenting the number and percentage of patients using each medication for each treatment group.

Calculated eGFR

The main safety endpoint is calculated eGFR.

Patients will be considered as “on treatment”, whilst they are taking their assigned randomized treatment. If a patient switches to an alternative treatment or stops taking their assigned randomized treatment, this data will be excluded from the summaries, figures and analysis for eGFR data.

Calculated eGFR as determined by the central lab will be summarized by visit. The calculated eGFR will be presented graphically to show the overlaid patient profiles and mean profile over time.

The following imputation method will be applied at each relevant timepoint for patients with missing eGFR values:

1. Patients that lose their graft before the timepoint in question will be assigned a value of zero for their missing eGFR value.
2. Patients that die or are lost to follow-up with a functioning graft before the timepoint in question will have an imputed value using the last-observation-carried-forward (LOCF) method.

Graft loss patients do not have a functioning graft, hence the lowest possible eGFR value (zero) will be assigned to such patients with missing eGFR values. In contrast, patients that die with a functioning graft, die for different reasons such as suicide, car accidents, cancer, therefore if they have a missing eGFR value, an imputed value using the LOCF method will be used. Similarly, patients who are lost to follow-up and have renal function, but are missing a Month 6 or Month 12 value for various reasons (e.g. moving from the area or not being able to make the site visit during the Month 6 or Month 12 visit) will have an imputed value using LOCF method for any missing eGFR value.

The mean eGFR results will be estimated from a longitudinal repeated measures mixed effects model using all the individual data collected until the timepoint of interest (1st IA Month 3 visit, 2nd IA Month 6 visit) whilst the patient is on treatment. From the model, estimates of the average at the timepoint of interest, treatment difference and 90% confidence

intervals will be obtained. The model will include fixed effects for treatment, time, donor age, donor type (living or deceased) and donor characteristic, treatment by time interaction and donor type by treatment by time interaction. An unstructured variance-covariance structure shall be used, however in the case that the model fails to converge, alternative structures would be tested. The estimates of the adjusted means and two-sided 90% CIs obtained from the model will be plotted over time.

The donor characteristic is a category that could have the result of “standard” or “expanded”.

Vital signs

All vital signs data will be listed by treatment, patient, and visit/time and if ranges are available abnormalities (and relevant orthostatic changes) will be flagged. Summary statistics will be provided by treatment and visit/time.

ECG evaluations

All ECG data will be listed by treatment, patient and visit/time, abnormalities will be flagged. Summary statistics will be provided by treatment and visit/time.

Clinical laboratory evaluations

All laboratory data will be listed by treatment, patient, and visit/time and if normal ranges are available abnormalities will be flagged. A separate listing is provided presenting all parameters in a patient with any abnormal values. Summary statistics will be provided by treatment and visit/time.

Special clinical laboratory evaluations

Coagulation parameters prothrombin time and partial thromboplastin time will be listed by treatment, patient and visit/time. The coagulation parameters will also be presented graphically to show the overlaid patient profiles and mean profile over time for each parameter separately. Additionally overlaid patient profiles and mean profile over time will be presented graphically for platelets.

Cytokine assessments via multiplex cytokine including TNFa, IFNg, IL1b, IL2, IL4, IL8, IL10, IL12p, IL70 and IL13 will be listed by treatment, patient, and visit/time. The cytokine assessments will also be presented graphically to show the overlaid patient profiles and mean profile over time for each parameter separately.

Donor specific antibodies will be listed by patient and visit.

Immunogenicity data consisting of anti-CFZ533 antibodies information will be listed by patient and visit.

Virology monitoring results for hepatitis B, hepatitis C, HIV, Epstein-Barr Virus (EBV), cytomegalovirus (CMV) and BK virus will be listed by patient, and visit/time and if normal ranges are available, abnormalities will be flagged. The frequency of EBV, CMV and BK virus will also be summarized by treatment.

Adverse events

All information obtained on adverse events will be displayed by treatment and patient.

AEs and infections collected are to be coded with the MedDRA dictionary that gives preferred term and primary system organ class information. AEs and infection preferred terms are to be analyzed as a whole under the heading of AEs. Depending on the number of AEs in Part 2, the incidence of AEs will be summarized by body system, severity and relationship to study drug by the following where possible:

- AEs by primary SOC and PT
- AEs rated to have relationship to study drug by SOC and PT
- AEs by primary SOC, PT, and maximum severity
- SAEs by SOC and PT
- SAEs rated to have relationship to study drug by SOC and PT
- Deaths by SOC and PT
- AEs leading to discontinuation of a study drug by SOC and PT
- AEs leading to dose adjustment or interruptions of a study drug by SOC and PT
- Infections by type of infection (viral, bacterial, fungal, and others) and microorganism of infection
- Serious infections by type of infection and micro-organism of infection
- New onset diabetes mellitus
- AEs by standardized MedDRA query (SMQ) levels (broad and narrow search)
- AEs by standardized MedDRA query (SMQ) and preferred term (broad and narrow search)

In all tables about incidence rates of AEs / Infections, if a patient has multiple occurrences of an AE, this patient will be counted only once in the corresponding AE category. If a patient has multiple adverse events within a system organ class, s/he will be counted only once for that class. If a patient has multiple severity ratings for an AE while on treatment, s/he is only counted under the maximum rating. In the tables, only adverse events occurring at or after first drug intake are included.

Information pertaining to AEs noted during the study will be listed by patient, including the verbatim term given by the investigator, the PT and SOC given by the MedDRA dictionary, start and end date, causality, severity, and relationship to study drug as assessed by the investigator.

BK-polyoma viremia and nephropathy

The following variables will be summarized by treatment and listed by treatment group and patient:

Occurrence of BK-polyoma viremia any time post-transplantation

Occurrence of BK-polyoma virus nephropathy any time post-transplantation

The difference of the investigational regimens to the control regimen will be summarized by risk ratios and appropriate CIs.

Tuberculosis surveillance

Tuberculosis (TB) test data collected will be listed by patient and visit.

Pregnancy test

Pregnancy test results for all females will be listed by patient and visit.

Desirability of outcome ranking (DOOR)

Composite endpoint:

- a) Survived; without graft loss and without tBPAR
- b) Survived; without graft loss and with tBPAR
- c) Survived; with graft loss and without tBPAR
- d) Survived; with graft loss and with tBPAR
- e) death

Long term renal function:

- a) Normal creatinine; without BK and without tBPAR

- b) Normal creatinine; with BK and without tBPAR
- c) Normal creatinine; without BK and with tBPAR
- d) Normal creatinine; with BK and with tBPAR
- e) Elevated creatinine; without BK and without tBPAR
- f) Elevated creatinine; with BK and without tBPAR
- g) Elevated creatinine; without BK and with tBPAR
- h) Elevated creatinine; with BK and with tBPAR

Where Normal creatinine is the most recent creatinine no higher than 25% above Nadir and Elevated creatinine is the most recent creatinine greater than 25% above Nadir

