3.1.4 Part 2 – Arms 2A-2B

Figure 3-3 Part 2 Design

Approximately 45 patients who meet the inclusion criteria will be randomized in a 2:1 fashion within 24 hours pre-transplant to receive one of the 2 treatment arms (Figure 3-3):

1. **Arm 2A**, n=30: Basiliximab 20 mg (Days 1, 4) + **CFZ533 at 10 mg/kg IV** (17 doses) + MMF 1.0g BID + CS
2. **Arm 2B Control/SoC**, n=15: Basiliximab 20 mg (Days 1, 4) + Tac (4-11 ng/mL) + MMF 1.0 g BID + CS

Induction therapy must be started within 2 hours prior to transplantation, or according to local practice.

The first dose of CFZ533 will be administered IV pre-transplant or intra-operatively. Drug administration will begin after randomization and must be completed by the time of unclamping. Subsequent doses of CFZ533 will be administered IV (Arm 2A), over a period of 12 months.

Other study drugs (apart from Basiliximab) should be started within 24 hours post-transplant. The second dose of basiliximab will be administered on Day 4, or according to local practice.

The day of randomization and transplant will be considered to be study Day 1. Further treatment will be given on study Days 3, 7, 15, 29, 43, 57 and then monthly thereafter until Months 12 (up to approximately Day 337). Subjects will then undergo Study Completion evaluations.

The primary endpoint of Part 2 will be assessed to determine whether the success criteria (safety and tBPAR) have been met

Corporate Confidential Information

Corporate Confidential Information

If notable AEs or safety concerns meeting the *a priori*-defined stopping criteria (see [Section 5.5.10](#)) one of the planned dose levels may be changed or discontinued via amendment.

Subjects will undergo Study Completion evaluations at the end of the trial.

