9.3.1 Study medication

The duration (days) of study medication administration will be summarized. This will be calculated by subtracting the date of the last administration of study medication from the date of first administration and then adding the dosing interval for CFZ533 or Tac (i.e., 28 days for treatment administered once every 4 weeks). In calculating the duration of treatment, days of temporary interruption of study medication for any reason will be included. Further, the frequency of dose changes (including temporary dose interruption) will be presented by reason for the change.

Average daily doses will be presented by treatment. “Zero” will be used for periods of temporary interruption of study medication for any reason.

The number and percentage of subjects who prematurely discontinued study medication will be summarized by reason for discontinuation.

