9.4 Analysis of the primary variable(s)

9.4.1 Variable(s)

Parts 1 and 2:

The primary variable is tBPAR after 3 months of treatment. For the analysis in Part 2, the total “on treatment time” in each treatment group is required.

Corporate Confidential
Information

Corporate Confidential Information

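### The treatment-duration rule subtracts the dates in the wrong order and does not say which dosing interval to add after a loading dose

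*SAP*

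**What the plan says.** SAP 7.1.2, under study medication, gives the derivation for a duration that is to be both summarized and listed: "The duration will be calculated by subtracting the date of the last administration of study medication from the date of first administration", "then adding the dosing interval for CFZ533". It gives no number for the interval and no rule for choosing one. Days of temporary interruption stay in the duration.

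Protocol 9.3.1 has the same order of subtraction: "This will be calculated by subtracting the date of the last administration of study medication from the date of first administration". Its interval is that of CFZ533 or Tac, with the gloss "i.e., 28 days for treatment administered once every 4 weeks". That is the only interval value stated for this rule in either document.

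The Part 2 schedule is in protocol 3.1.4. After Day 1, "Further treatment will be given on study Days 3, 7, 15, 29, 43, 57 and then monthly thereafter until Months 12", with the last dose at about Day 337. Protocol 3.3 places the start of four-weekly dosing at Day 57. Protocol 5.2 and SAP 1.4.2 give 17 doses for Arm 2A.

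**The concern.** Subtracting the last date from the first gives zero or a negative number, so the rule as written cannot return a correct duration for anyone with more than one dose. Correcting the order does not complete the rule. CFZ533 is given at several different intervals in Part 2, and the text refers to one interval without saying which. Two programmers working independently could report different durations for the same patient who stopped in the loading phase.

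The stake is the reported exposure in Arm 2A, planned at 30 patients. Early stopping is a real feature of this trial: SAP 6.1.4 records that some patients had been switched from their randomized treatment.

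**Working it through.** **Inputs**

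- Order of subtraction: SAP 7.1.2 and protocol 9.3.1.
- Dosing days, Part 2: 1, 3, 7, 15, 29, 43, 57, then every 28 days to 337 (protocol 3.1.4; a study month is 28 days in protocol 3.1.2).
- The only stated interval: 28 days, for four-weekly dosing (protocol 9.3.1).
- Planned doses in Arm 2A: 17.
- Study completion: Day 364 (protocol Appendix 1, Part 2 blood log).

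**Check of the calendar.** Days 1 to 57 hold 7 doses. Days 85 to 337 in steps of 28 hold (337 − 85)/28 + 1 = 10. The total is 17, which reproduces the documents' figure. The documents give no duration figure to reproduce.

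**Gaps between doses.** 2, 4, 8, 14, 14, 14, then 28 throughout: five distinct values.

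**Formulas**, with the first dose on Day 1, the last on Day L and interval I:

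- As written: 1 − L + I
- Order corrected: L − 1 + I

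Each is computed once with I = 28 and once with I equal to the scheduled gap after Day L. No dose follows Day 337, so 28 is used there as an assumption.

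| Last dose (Day L) | Scheduled gap after L | As written, I = 28 | As written, scheduled I | Corrected, I = 28 | Corrected, scheduled I | Difference between the last two |
|---|---|---|---|---|---|---|
| 1 | 2 | 28 | 2 | 28 | 2 | 26 |
| 3 | 4 | 26 | 2 | 30 | 6 | 24 |
| 7 | 8 | 22 | 2 | 34 | 14 | 20 |
| 15 | 14 | 14 | 0 | 42 | 28 | 14 |
| 29 | 14 | 0 | −14 | 56 | 42 | 14 |
| 43 | 14 | −14 | −28 | 70 | 56 | 14 |
| 57 | 28 | −28 | −28 | 84 | 84 | 0 |
| 337 | 28 | −308 | −308 | 364 | 364 | 0 |

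Three results follow.

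1. As written, every last dose on Day 29 or later gives zero or less under either choice of interval. Earlier stoppers get values of zero or above. These are still wrong, except for a patient dosed on Day 1 only, where the order makes no difference.
2. With the order corrected, a completer has 337 − 1 + 28 = 364 days, which agrees with the Day 364 completion visit.
3. With the order corrected, the choice of interval matters only for last doses on Days 1 to 43, by 14 to 26 days per patient. In a summary of 30 patients, one such patient moves the arm mean by 14/30 = 0.5 to 26/30 = 0.9 days.

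**The case against.** The reversed order is plainly a slip of wording. A completer at −308 days would be noticed at the first output, and CFZ533 administrations are also listed by patient, so actual dosing stays visible. That limits the practical harm, but a derivation rule in an analysis plan should be right as written.

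A reader might go further in four ways. The documents do not support any of them.

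- **That the rule overstates the exposure of patients who stop in the loading phase.** This is true only if 28 days is added after every dose. The SAP states no value, and the protocol ties 28 days to four-weekly dosing. The protocol's sentence also covers Tac, which protocol 5.5.4 has given twice daily, so the interval is evidently meant to follow the schedule. On that reading the excess is zero. What is missing is a statement of which convention applies. A declared flat convention would also be legitimate.
- **That the rejection analysis is affected.** Protocol 9.4.1 says that total on-treatment time "in each treatment group is required" for the Part 2 analysis. The text after it is redacted, and nothing visible says that the 9.3.1 duration supplies that time. The supportive Poisson model in SAP 6.1.4 uses its own follow-up time, censored at switch or discontinuation. For eGFR, SAP 7.1.2 defines on-treatment status by whether the assigned treatment is being taken.
- **That average daily dose is distorted in proportion.** Neither document says that this duration is its denominator.
- **That one rule should govern on-treatment time everywhere.** That would override the Poisson model's censoring and a window that cannot be seen.

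**Conclusion.** The point holds as a minor one. The subtraction is reversed in both documents. Applied literally, it gives zero or negative durations for Part 2 CFZ533 patients whose last dose is on Day 29 or later, and −308 instead of 364 days for a completer with a 28-day interval. Separately, the interval to add after a loading dose is undefined. The two natural choices differ by 14 to 26 days for last doses on Days 1 to 43 and agree from Day 57.

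The figures assume dosing on the nominal days and 28 days after the Day 337 dose. How many patients stopped in the loading phase is not given, so the total effect on the exposure table cannot be stated. The effect shown is confined to the descriptive exposure summary and listing. No tBPAR or eGFR analysis visible in the documents uses this duration.

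**What to change.** In SAP 7.1.2 and protocol 9.3.1, replace the rule by: duration = date of last administration − date of first administration + the scheduled dosing interval that follows that last dose in the applicable schedule. For Part 2 CFZ533 the interval is 2, 4, 8, 14, 14 and 14 days after Days 1, 3, 7, 15, 29 and 43, and 28 days from Day 57, including after the final dose. Alternatively, correct the order and state explicitly that a flat 28 days is intended for CFZ533.

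Protocol 9.3.1 also covers Part 1 and Tac, so its wording should point to the schedule that applies (Part 1, Part 2 or Tac) and not list Part 2 days alone. It should also name the interval to use after the last scheduled dose, where no next dose exists. Leave the separate on-treatment definitions for tBPAR and eGFR as they are.

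The cost is one sentence in each document. No new data are needed, and nothing in dosing or conduct changes.

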3.1.2 All cohorts

Before any study-related evaluations are performed, the patient must give written informed consent. Once consent is obtained, pre-transplant screening and baseline assessments will occur to determine the patient's eligibility to participate in the study starting up to 28 days prior to transplantation. If the screening, baseline and study Day 1 visits occur in close proximity of each other (i.e., within a 12 hour timespan), certain repeated assessments may be omitted, as noted in the [Assessment schedule](#). Data collection from assessments performed at the clinical site as part of medical standard of care but prior ICF sign-off is acceptable in order to confirm patient eligibility for patients receiving an organ from a deceased donor, if assessed shortly before transplantation (i.e within 24h – matching the baseline window of Day -1 to Day 1) and in-line with inclusion and exclusion criteria.

Day 1 is defined as the day of randomization/enrollment and transplantation. This protocol defines 7 days to a week and 4 weeks (or 28 days) to a Study Month. For example, Week 2 is considered to start on Day 8 and Study Month 2 is considered to start on Week 5/Day 29. Randomization/enrollment should occur within 24 hours pre-transplant and drug administration will begin after randomization/enrollment. If CFZ533 is to be administered, the first dose of CFZ533 will be administered IV pre-transplant or intra-operatively, and must be completed by the time of unclamping. Other study drugs must be started within 24 hours post-transplant or according to local practice.

Patients who are randomized/enrolled but not transplanted will be replaced. All randomized/enrolled subjects are expected to continue in the study up to Month 6 (Part 1) or Month 12 (Part 2) regardless of being on or off randomized/assigned treatment. All subjects will be followed-up for safety (e.g., SAEs) for approximately three months after their last dose of CFZ533 or 2 months after the EoS visit for patients on SoC treatment.

[figure not shown]
Any treatment arm in which the rejection rate fulfills the *a priori* defined stopping rules (see [Section 5.5.10](#)) will be immediately discontinued at any time during the study.

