To further minimize the risk for over immunosuppression, no basiliximab induction therapy will be administered to patients participating in this part of the trial. Patients will also receive prophylaxis for CMV and PCP and recipients with negative EBV serology will be excluded. Upon completion of the final CFZ533 dose administration, patients will remain on SoC to be managed based on defined local practices and will be monitored through Month 6 per the study protocol.

Dose selection for Part 2: In Part 2 of this trial, CFZ533 will be investigated at 10 mg/kg IV (a loading regimen consisting of 7 doses is being used in the first 2 months, then monthly (q4w) dosing starting on study Day 57). Corporate Confidential Information

PK and PD data of ASKP1240 has been published for NHP ([Ma et al 2014](#)) and for healthy volunteers ([Goldwater et al 2013](#)) and some data have been revealed for a Phase 2 clinical trial in kidney transplant ([Harland et al 2015](#)). Corporate Confidential Information

Corporate Confidential Information

Data from ASKP1240, a monoclonal antibody blocking CD40: At the American Transplant Congress 2015, preliminary data from a Ph II trial in kidney transplantation (Harland et al Abstract ATC 2015), suggested efficient target mediated clearance of ASKP1240 during the first two months post-transplantation, Corporate Confidential Information

Corporate Confidential Information

Part 1 PK/PD data in transplanted patients will be analyzed prior to start Part 2. Any relevant deviations in the CFZ533 PK or CD40 occupancy profile for 3 mg/kg IV/SC measured in Part 1 of this trial Corporate Confidential Information will be modeled to further support the 10 mg/kg IV regimen prior to the initiation of Part 2. Any further dose or regimen adjustments will be implemented via amendment.

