1.4.2 Part 2 – Arms 2A-2B

Approximately 45 patients who meet the inclusion criteria will be randomized in a 2:1 fashion within 12 hours pre-transplant to receive one of the 2 treatment arms:

1. Arm 2A, n = 30: Basiliximab 20 mg (Days 0, 4) + CFZ533 at 10 mg/kg IV (17 doses) + MMF 1.0 g BID + CS
2. Arm 2B Control/SoC, n = 15: Basiliximab 20 mg (Days 0, 4) + Tac (4-11 ng/mL) + MMF 1.0 g BID + CS

Induction therapy must be started within 2 hours prior to transplantation, or according to local practice.

The first dose of CFZ533 will be administered IV pre-transplant or intra-operatively. Drug administration will begin after randomization and must be completed by the time of unclamping or up to 6 hours prior to the time of unclamping. Subsequent doses of CFZ533 will be administered IV (Arm 2A), over a period of 12 months.

Other study drugs must be started within 24 hours post-transplant. The second dose of basiliximab will be administered on Day 4, or according to local practice.

[figure not shown]
The day of randomization and transplant will be considered to be study Day 1.

Patients will then undergo Study Completion evaluations.

The primary endpoint of Part 2 will be assessed to determine whether the success criteria (safety and tBPAR) have been met when all patients have completed the Month 3 visit. If it is found that the data up to the Month 3 visit is inconclusive, a reevaluation (interim analysis) will occur after the Month 6 visit.

If the stopping rules are not met and the primary endpoint of Part 2 is fulfilled at Month 3, Part 3 (exposure-response profiling) will be initiated following consultation of the DMC. Cumulative efficacy and safety data will be collected on an ongoing basis during the conduct of the study.

Figure 1-2 Part 2 Design

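### Average daily dose is a poor summary of front-loaded CFZ533: the denominator is undefined, and with time on treatment as denominator the figure is inflated for most early stoppers

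*SAP*

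**What the plan says.** SAP section 7.1.2, Study medication: "Average daily doses of each treatment will be presented in a summary table and will be listed by treatment and patient". Protocol section 9.3.1: "Average daily doses will be presented by treatment". Protocol section 9.3.2 deals separately with average daily MMF, tacrolimus and corticosteroid doses, so the study-medication statement is not confined to the daily oral drugs. It takes in CFZ533.

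The Arm 2A regimen is given in SAP section 1.4.2 as "CFZ533 at 10 mg/kg IV (17 doses", and the days are in protocol section 3.1.4: "Further treatment will be given on study Days 3, 7, 15, 29, 43, 57 and then monthly thereafter until Months 12". The same section puts the last dosing day at about Day 337. Protocol section 3.3 describes "a loading regimen consisting of 7 doses is being used in the first 2 months, then monthly (q4w) dosing starting on study Day 57". Protocol section 5.5.5 allows no change to the CFZ533 dose other than for body weight.

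Neither document says what the average is divided by. Both define treatment duration as the span between first and last administration plus one dosing interval. The protocol illustrates that interval as 28 days for four-weekly treatment; the SAP gives no value. Both count temporary interruptions as zero dose, and neither says how time after a permanent stop is handled.

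**The concern.** An average per day suits a drug taken every day. CFZ533 is infused at intervals of 2 to 14 days up to Day 57 and 28 days after that, at a fixed mg/kg dose. Among patients who miss no infusion, the average therefore depends only on when they stopped and on the denominator chosen. It says nothing about how well the schedule was followed.

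Early stopping is a realistic possibility. SAP section 6.1.4 records that data review found patients who had been moved off their randomized treatment, without naming the arm. The visible exposure text plans no summary of infusions received, cumulative dose or share of scheduled infusions given, so average daily dose is its only summary of the amount of CFZ533 administered. A table whose mean goes up when patients leave during the loading phase would be easy to misread in a study meant to inform regimen selection (protocol section 1.2).

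**Working it through.** **Inputs.** The dose is 10 mg/kg per infusion (SAP 1.4.2). The infusion days are 1, 3, 7, 15, 29, 43 and 57, then every 28 days to Day 337 (protocol 3.1.4 and 3.3; protocol 3.1.2 sets "4 weeks (or 28 days) to a Study Month"). I assume constant weight, no missed infusions and averages in mg/kg. I take duration as last date minus first date, the evident intent of the wording.

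**Reproducing the plan's count.** There are 7 infusions up to Day 57. Days 85 to 337 in steps of 28 give (337 − 85)/28 + 1 = 10 more. The total is 17, as stated, with 7 in the loading phase, as stated.

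**Formula.** After k infusions, average daily dose = 10k / duration, where duration = (day of last infusion − 1) + added interval. Three denominators were tried: (a) the protocol's 28-day interval; (b) the interval to the next scheduled infusion; (c) a fixed 364 days.

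| Infusions (last day) | (a) 28-day interval | (b) to next infusion | (c) fixed 364 days |
|---|---|---|---|
| 1 (Day 1) | 10/28 = 0.36 | 10/2 = 5.00 | 0.03 |
| 3 (Day 7) | 30/34 = 0.88 | 30/14 = 2.14 | 0.08 |
| 4 (Day 15) | 40/42 = 0.95 | 40/28 = 1.43 | 0.11 |
| 5 (Day 29) | 50/56 = 0.89 | 50/42 = 1.19 | 0.14 |
| 7 (Day 57) | 70/84 = 0.83 | 70/84 = 0.83 | 0.19 |
| 10 (Day 141) | 100/168 = 0.60 | 100/168 = 0.60 | 0.27 |
| 17 (Day 337) | 170/364 = 0.47 | 170/364 = 0.47 | 0.47 |

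**Ratios to a completer.**
- Stop after Day 57: (70/84)/(170/364) = 1.78 under both (a) and (b).
- Stop after Day 15, with 4/17 = 24% of the planned drug: 0.952/0.467 = 2.04 under (a) and 1.429/0.467 = 3.06 under (b).
- One infusion only: 0.357/0.467 = 0.76 under (a) and 5.00/0.467 = 10.7 under (b).

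**Arm mean if 30% stop early and 70% complete (assumption).**
- All stop after Day 15, (a): 0.7 × 0.467 + 0.3 × 0.952 = 0.61, 31% above 0.467.
- All stop after Day 15, (b): 0.7 × 0.467 + 0.3 × 1.429 = 0.76, 62% above.
- All stop after Day 57, (a) or (b): 0.7 × 0.467 + 0.3 × 0.833 = 0.58, 24% above.

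**One skipped maintenance infusion in a patient who otherwise completes.** 160/364 = 0.44, which is 6% lower. The figure barely registers a missed infusion, and stopping early moves it much more.

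**The case against.** The strongest objection is that the on-treatment denominator is an inference. Over a fixed 364 days the figure rises with every infusion received and the problem disappears. That is arithmetically right, but the documents do not ask for a fixed period. The only time span they define here is an on-treatment duration, and zero dose is assigned only to temporary interruptions. On-treatment averaging is therefore the natural reading, and a choice that reverses the ranking of patients should not be left to programming.

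A reader might go further and infer that the average always rises the earlier a patient stops, or that the least-treated patients come out as the most intensively dosed. The documents do not support that. With the protocol's 28-day interval the figure peaks at the fourth infusion and then declines, and a patient with one infusion has the lowest value of all. The strictly increasing pattern, and the 5.00 after one infusion, need the interval to the next scheduled infusion, which neither document specifies.

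Nor would the table state the opposite of the truth. An on-treatment average is a rate, and patients treated only during loading did receive more drug per day while treated. The error would lie in reading that rate as total exposure or compliance.

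Early stopping also stays visible. SAP section 7.1.2 lists CFZ533 administration, summarises duration, tabulates discontinuations and dose changes by reason, and plans a Kaplan-Meier curve of time to discontinuation if events allow. Protocol section 6.4 treats concentrations and PK parameters as the exposure measures. All of this limits the harm. It does not supply a usable summary of the amount of CFZ533 given.

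**Conclusion.** The point holds as a low-priority improvement. With an on-treatment denominator, average daily dose is inflated for most early stoppers: 1.78 times the completer's value after Day 57 under either interval convention, and 2.0 to 3.1 times after Day 15. An arm with 30% early stopping would show a mean 24% to 62% above full compliance across the scenarios examined. The 30% and the stopping days are assumptions, and the upper end depends on the interval convention. The direction is not uniform across all stopping times and reverses over a fixed 364 days, so the undefined denominator is part of the defect. The consequence is confined to a descriptive exposure table. Nothing in the visible text feeds this figure into the primary analysis, another endpoint or a stopping rule.

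**What to change.** In SAP section 7.1.2, for CFZ533, replace average daily dose with:
- the number of infusions received;
- the cumulative dose in mg/kg;
- the percentage of scheduled infusions received by Months 3, 6 and 12, for all treated patients, with the denominator counted to the cut-off and not to the patient's stopping day. Counted to the stopping day, it would be 100% for anyone who stopped early without missing an infusion.

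State the study day for each cut-off. Twelve 28-day study months end on Day 336, one day before the last scheduled infusion, so an unstated Month 12 could mean 16 or 17 scheduled infusions.

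Keep average daily dose for MMF and tacrolimus, and state its denominator, including how time after permanent discontinuation is treated.

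The cost is SAP wording and some table programming. The infusion records are already collected, and no endpoint, dose or clinical rule changes.
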